- If you get any side effects, talk to your doctor, pharmacist or nurse. This includes any possible side effects not listed in this leaflet. See section 4.

What is in this leaflet

1. What Fotivda is and what it is used for
2. What you need to know before you take Fotivda
3. How to take Fotivda
4. Possible side effects
5. How to store Fotivda
6. Contents of the pack and other information

1. What Fotivda is and what it is used for

The active substance in Fotivda is tivozanib, which is a protein kinase inhibitor. Tivozanib reduces the supply of blood to the cancer, which slows down the growth and spread of cancer cells. It works by blocking the action of a protein called vascular endothelial growth factor (VEGF). Blocking the action of VEGF prevents the formation of new blood vessels.

Fotivda is used to treat adults with advanced kidney cancer. It is used where other treatments such as interferon-alpha or interleukin-2 have either not yet been used or have not helped to stop your disease.

2. What you need to know before you take Fotivda

Do not take Fotivda:

- If you are allergic to tivozanib or any of the other ingredients of this medicine (listed in section 6);
- If you are taking St. John's Wort (also known as *Hypericum perforatum*, a herbal remedy used for treatment of depression and anxiety).

Warnings and precautions

Talk to your doctor, pharmacist or nurse before taking Fotivda:

- if you have **high blood pressure**
Fotivda can increase your blood pressure. Your doctor will monitor your blood pressure regularly and, if it is too high, may either give you a medicine to lower it, or reduce your dose of Fotivda. However, if your blood pressure remains too high, your doctor may decide to interrupt or to stop treatment with Fotivda. If you are already taking a medicine to treat high blood pressure, and your doctor reduces the dose of Fotivda or interrupts or stops treatment, you will be regularly checked for low blood pressure.
- if you have or have had an aneurysm (enlargement and weakening of a blood vessel wall) or a tear in a blood vessel wall.

KEY INFORMATION

What is Fotivda and what it is used for

- Fotivda is a medicine for treating adults with advanced kidney cancer. Fotivda may be used in previously untreated patients or in those whose disease has got worse despite treatment with another medicine that works in a different way.
- Fotivda does not cure advanced kidney cancer.
- Fotivda may increase how long people live without their disease getting worse. However, it does not cure advanced kidney cancer.

For further information about Fotivda and its uses, see section 1.

What you need to know before you take Fotivda

- Do not take Fotivda if you are allergic to the active ingredient, tivozanib, or if you are taking St. John's Wort (a herbal remedy for depression).
- Talk to your doctor if you have high blood pressure, have had an aneurysm (a bulge in a blood vessel), have had blood clots or have any of the signs or symptoms of heart failure.

For further information, see section 2.

Most important side effects with Fotivda

- The most common side effect with Fotivda is high blood pressure (which occurs in almost half of patients and can be serious in a quarter of patients).
- Other common side effects are voice changes, tiredness and diarrhoea (which occur in about a quarter of patients).

For the full list of possible side effects, see section 4.

To understand all information about using this medicine, it is very important that you read the rest of this leaflet.

Key information about Fotivda for renal cell carcinoma (kidney cancer)

What is Fotivda and what is it used for:

- Fotivda (tivozanib) is a medicine to treat adults with advanced kidney cancer that has come back after previous treatment or has spread to another part of the body.
- Fotivda does not cure advanced kidney cancer.
- Fotivda may increase the time until a test shows the cancer has grown or spread, but it has not been shown to extend how long people live.

Benefits and side effects of Fotivda:
 In a study involving 517 people, Fotivda was compared to sorafenib, a standard treatment for kidney cancer. What difference did Fotivda make?

	Fotivda	Standard treatment
How long did people live?	People given Fotivda lived 2.6 months less . However, this finding may be due to chance.	28.2 months vs 30.8 months
How did people feel?	People given Fotivda felt 1.1 points worse on a 108-point scale. However, this finding may be due to chance	4.8 points worse vs 3.7 points worse
How long did people have before the cancer grew or spread?	People given Fotivda had 2.8 months longer before the cancer grew or spread.	11.9 months vs 9.1 months
How common were serious side effects?	People given Fotivda had 6% fewer serious side effects (disabling, life-threatening, or requiring hospitalization).	64% vs 70%

Note: Left panel shows the standard patient leaflet for tivozanib (control); upper right panel shows the EMA's proposed key information section with qualitative statements; lower right panel shows the key information section containing both qualitative and quantitative information.

----- end of page-----

Section A: Previous experience using the patient leaflet

1. If you are currently prescribed or have ever been prescribed a medicine, how often do you read the patient leaflet?
 - Often
 - Sometimes
 - Rarely
 - Never
2. If you are currently prescribed or have ever been prescribed a medicine, how often do you talk to your doctor about the information you see in the patient leaflet?
 - Often
 - Sometimes
 - Rarely
 - Never

----- end of page-----

Section B: Participants' expectations and understanding of treatment using the patient leaflet

Imagine that your doctor prescribes you a new medicine. When you pick up the medicine from the pharmacy, you read the patient leaflet included in the box.

This patient leaflet is for a medicine called Fotivda. You can zoom in and scroll through every page of the leaflet. You can also download it here: [Fotivda.pdf](#)

You will be shown the patient leaflet for Fotivda on every page for the next few questions, along with an option to download the leaflet. Please use the information in the leaflet to answer the questions.

----- end of page-----

3. This first question is practice. Scroll to section 3 of the leaflet and find the first word.
 - Always **[correct]**
 - Serious
 - Patient
 - Chance

----- end of page-----

4. What is Fotivda used for?
 - To treat adults with breast cancer
 - To treat adults with heart failure
 - To treat adults with advanced kidney cancer **[correct]**
 - To treat adults with advanced lung cancer
 - Not sure

----- end of page-----

5. Does Fotivda cure advanced kidney cancer?
 - Definitely yes
 - Probably yes
 - Probably no
 - Definitely no

----- end of page-----

6. Do people with advanced kidney cancer live longer when treated with Fotivda?
 - Definitely yes
 - Probably yes
 - Probably no
 - Definitely no

----- end of page-----

7. Do people with advanced kidney cancer feel better when treated with Fotivda?

- Definitely yes
- Probably yes
- Probably no
- Definitely no

----- end of page-----

8. Compared to standard treatment, how long did people given Fotivda live? **[Key information table group]**

- 6 months **less** than people given standard treatment
- 2.6 months **less** than people given standard treatment **[correct]**
- About the same as people given standard treatment
- 2.6 months **longer** than people given standard treatment
- 6 months **longer** than people given standard treatment
- Not sure

----- end of page-----

9. Overall, how large are the benefits of Fotivda?

- Very large
- Large
- Moderate
- Small
- Very small to none

----- end of page-----

10. To confirm that the survey is functioning correctly, please select 'Standard treatment', below.

- Fotivda
- Advanced kidney cancer
- Standard treatment **[correct]**
- Neither Fotivda or standard treatment

----- end of page-----

11. Compared to standard treatment, how common were serious side effects with Fotivda? **[Key information table group]**

- 22% **less** common than with standard treatment
- 6% **less** common than with standard treatment **[correct]**
- About the same as standard treatment
- 6% **more** common than with standard treatment
- 22% **more** common than with standard treatment
- Not sure

----- end of page-----

12. What is the most common serious side effect of Fotivda?

- Rapid or irregular heart beat
- High blood pressure **[correct]**

- Diarrhoea
- Muscle spasms
- Not sure

----- end of page-----

13. How concerning are the side effects of Fotivda?

- Extremely concerning
- Very concerning
- Somewhat concerning
- Not at all concerning

----- end of page-----

14. Do you think the benefits of Fotivda outweigh the side effects?

- Definitely yes
- Probably yes
- Probably no
- Definitely no

----- end of page-----

15. What is the recommended dose of Fotivda during the first 3 weeks of treatment? **[All groups]**

- One 890 microgram capsule daily
- One 1340 microgram capsule daily **[correct; answer in section 3 of PIL]**
- Two 1340 microgram capsules daily
- Two 890 microgram capsules daily
- Not sure

----- end of page-----

Section C: Participants' satisfaction with the patient leaflet

You're almost done. What was your experience of using the patient leaflet for Fotivda?

16. Was it easy to find information about Fotivda using the leaflet?

- Very easy
- Easy
- Difficult
- Very difficult

17. Was it easy to understand the information?

- Very easy
- Easy
- Difficult
- Very difficult

Please rate your agreement with the following statements.

18. The leaflet helped me think about the benefits of Fotivda.

- Strongly agree
- Agree
- Disagree
- Strongly disagree

19. The leaflet helped me think about the side effects of Fotivda

- Strongly agree
- Agree
- Disagree
- Strongly disagree

20. The leaflet helped me think of questions I would like to ask my doctor

- Strongly agree
- Agree
- Disagree
- Strongly disagree

21. Overall, did you find the patient leaflet for Fotivda:

- Very helpful
- Helpful
- Unhelpful
- Very unhelpful

----- end of page-----

Section D: Demographics

Thank you for taking the time to respond to this survey. These last 5 questions are to help us better understand you.

22. How old are you?

- 18 to 24
- 25 to 44
- 45 to 64
- 65 and older

23. What is your sex?

- Male
- Female
- Other

24. What is the highest level of education that you have completed?

- Less than 5 GCSE's A* to C (or equivalent i.e., level 1 diploma/ certificate /BTEC /NVQ)
- 5 or more GCSE's A* to C (or equivalent i.e., level 2 diploma/ certificate/ BTEC/ NVQ, O-Levels)
- 2 or more A-Levels (or equivalent i.e., level 3 diploma/ certificate/ BTEC)
- Undergraduate degree or higher

25. What is your approximate yearly income?

- Less than £20,000
- £20,000 to £34,999
- £35,000 to £44,999
- £45,000 and above

26. Have you, a close friend, or immediate family member (i.e. your partner, parents, siblings, or children) ever been diagnosed with cancer? (Select as many that apply)

- I have been diagnosed (currently, or in the past)
- An immediate family member has been diagnosed with cancer
- A close friend has been diagnosed with cancer
- To my knowledge, none of my close friends or family, or myself, has been diagnosed with cancer

----- end of page-----

----- end of survey message -----

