For tivozanib, the primary endpoint of the pivotal study was progression-free survival. To reduce confusion with overall survival, we described progression-free survival in plain language as "*how long did people have before the cancer grew or spread*", while overall survival was described as "*how long did people live?*".¹⁸ Because the improvement in overall survival was not statistically significant between tivozanib and sorafenib at the time of approval, we reported the absolute difference between the two treatment in the corresponding column of the table but noted that the observed difference may be due to chance.

For data on quality of life, we used any measure of global health-related quality of life reported in the EPAR, given that quality of life outcomes are inconsistently measured and reported in cancer drug trials.¹⁹ In the case of tivozanib, quality of life was measured using a 108-point scale. Because the difference in quality of life between tivozanib and sorafenib was not statistically significant, we reported the absolute difference in the table but noted that the observed difference may be due to chance.

The final outcome reported in the table is the percentage of patients who experienced severe side effects. Severe side effects were defined as grade 3 (severe events requiring hospitalization or prolongation of hospitalization) and grade 4 (life threatening) adverse events, according to the common terminology criteria for adverse events (CTCAE). We reported the overall proportion of patients who experienced these adverse events rather than the proportion determined to be treatment related by trial investigators. We excluded grade 5 adverse events (death) since these were relatively rare and could be misinterpreted.

Drug information

Tivozanib (Fotivda) was approved by the EMA in 2017 for the treatment of advanced kidney cancer. The primary outcome of the clinical trial that supported tivozanib's approval showed an additional benefit in progression-free survival of 2.8 months compared to sorafenib (11.8 months vs 9.1 months). Overall survival and overall health related quality of life were secondary outcomes in the trial but neither showed a statistically significant difference between the two treatments. Severe harms (defined as life threatening or requiring hospitalization [grade 3 and 4]) were more common with tivozanib (70%) than with sorafenib (64%).

References

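### The side-effect row in the quantitative key information table states a 6-point difference with no chance note, although the documents' figures suggest it is not statistically significant

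*Combined protocol and SAP*

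**What the plan says.** Figure 1 (lower right panel) shows the key information section for the group that receives both qualitative and quantitative information. It introduces the table with "In a study involving 517 people, Fotivda was compared to sorafenib, a standard treatment for kidney cancer". Four outcome rows follow.

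- **Overall survival:** 2.6 months less with Fotivda, with a note that this could be chance.
- **Quality of life:** 1.1 points worse, with the same note.
- **Progression-free survival:** 2.8 months longer, no note.
- **Serious side effects:** "People given Fotivda had 6% fewer serious side effects (disabling, life-threatening, or requiring hospitalization"), given as 64% versus 70%, no note.

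The appendix (eMethods, development of the section with qualitative and quantitative information) explains the note for two outcomes. For survival the reason begins "Because the improvement in overall survival was not statistically significant between tivozanib and sorafenib at the time of approval". For quality of life, where the difference was again not significant, the authors write "we reported the absolute difference in the table but noted that the observed difference may be due to chance". On side effects it says only how the figure was built: "We reported the overall proportion of patients who experienced these adverse events rather than the proportion determined to be treatment related by trial investigators". It gives no test, p value or interval for side effects, and no reason for leaving the note out.

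The Drug information paragraph of the appendix gives the same two rates the other way round: severe harms "were more common with tivozanib (70%) than with sorafenib (64"%).

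**The concern.** A reader who sees two rows marked as possibly due to chance will tend to take an unmarked row as established. If the side-effect difference is no better supported statistically than the two marked ones, the table treats like results differently.

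The row is the only comparative safety statement in this group's key information section. It bears on two items listed under Secondary outcomes: whether the side effects are seen as not concerning (question 13) and whether the benefits are seen to outweigh them (question 14). Part of any shift in the quantitative group on these items could then reflect unwarranted certainty in one cell rather than the value of quantitative information. The appendix itself names uncertainties among the things that patients need to be told.

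**Working it through.** **Inputs.** The rates of 64% and 70% and the total of 517 people are in Figure 1. Arm sizes and safety denominators are not in the documents, so an equal split (258.5 per arm) is assumed first and then varied.

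**The displayed figure.** 64% - 70% = -6 percentage points, so the row's difference reproduces from its own rates.

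**Test (pooled two-proportion z, two-sided).**
- Pooled rate: (0.64 + 0.70)/2 = 0.67.
- Standard error: √[0.67 × 0.33 × (1/258.5 + 1/258.5)] = 0.0414.
- z = 0.06/0.0414 = 1.45, p = 0.147.

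**95% confidence interval (unpooled).**
- Standard error: √[(0.64 × 0.36 + 0.70 × 0.30)/258.5] = 0.0413.
- 6.0 ± 1.96 × 4.13 = -2.1 to 14.1 points for the size of the gap.

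**Sensitivity to what is not given.**

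| Variation | Two-sided p |
|---|---|
| Whole-number counts, 259 and 258, chi-square | 0.14 to 0.15 |
| Same, continuity-corrected | 0.17 to 0.18 |
| Same, Fisher exact | 0.16 |
| 2:1 split, either direction | 0.17 |
| 3:1 split, either direction | 0.20 to 0.21 |
| Any split from 50/467 to 467/50, rates as printed (minimum) | 0.146 |
| Most favourable rounding, 63.5% vs 70.5%, equal split | 0.09 |
| Smallest p over whole-number counts that round to 64% and 70% (150/236 vs 198/281) | 0.096 |

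No variant reaches 0.05. If the safety population was smaller than 517, the same percentages would give a larger p. For a 6-point gap to reach p = 0.05 with equal arms, the number needed per arm is 1.96² × 2 × 0.67 × 0.33/0.06² ≈ 472, or about 944 in all.

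**Direction.** Swapping the rates (70% for tivozanib, 64% for sorafenib, as in the Drug information paragraph) changes only the sign of z. At an equal split p is still 0.147. The missing note is therefore a separate matter from the conflict over direction.

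**Where the row reaches.** The primary outcome is built from questions 5 to 7 (cure, survival, feeling better), none of which asks about side effects. Question 11, put only to this group, keys the 6% figure as correct. Question 8 keys the 2.6-month survival figure as correct and 'about the same' as wrong, although that row does carry the note. The comprehension items thus score reading of the displayed estimate, and adding a note would not by itself alter the key to question 11.

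**The case against.** The strongest reply is that no stated rule is broken. The appendix explains the note for two named outcomes and lays down no general rule for the table. That stands: this is uneven practice, not a breach.

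It is also fair to say that non-significance is calculated here and not reported. The data come from European Public Assessment Reports, which may hold denominators or a test that the documents omit. The result is robust to split and rounding, but the source could still settle the matter differently.

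A reader might infer more than the documents support:

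- *That this row is all the safety information the group sees.* It is not. The group receives a leaflet that contains the key information section, and the Procedure section says that the most common serious side effect can be found in the standard leaflet.
- *That every benefit is hedged and only the harm is not.* The progression-free survival row is a benefit row and has no note either, so a claim that the benefit-harm balance in question 14 is distorted cannot rest on that contrast.
- *That question 11 is mis-scored for want of the note.* Question 8 shows that a row with the note is still keyed on its point estimate. Question 11 also enters no comparison between groups.
- *That the primary result is at risk.* Questions 5 to 7 do not touch side effects.

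Finally, randomisation still gives a valid comparison of the leaflets as worded. That also stands. The point concerns what the quantitative leaflet represents, and the documents offer no basis for putting a size on any shift in questions 13 or 14.

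**Conclusion.** The point holds in limited form. The side-effect row presents as settled a difference that, on the figures in the documents, meets the condition for which the appendix attached a chance note to two other rows: p = 0.15, with an interval of -2.1 to 14.1 points, and a minimum p of about 0.09 under the most favourable rounding. This rests on 517 being at or above the safety denominator, on arm sizes that are not given (no split tried changes the conclusion), and on the percentages being rounded to whole numbers. It does not show that the two drugs have equal rates, since the interval allows a gap of up to 14 points.

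The consequence is confined to the quantitative group's answers to questions 13 and 14, and its size is unknown. Severity is minor to moderate. The conflict over direction in the same row must be resolved first, because a chance note added to a row whose direction is unsettled could leave a reversed statement in place. The documents do not show which direction is right.

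**What to change.** Before fielding, in this order:

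1. Reconcile the Drug information paragraph of the appendix, the side-effect row in Figure 1 and the key to question 11 against the source report, so that all three agree on which drug had 70% and which 64%.
2. Add to the side-effect row the chance sentence already used in the survival and quality-of-life rows, unless the source reports a significant difference. If it does, cite that result in the appendix.
3. State in the appendix that the note applies to every row whose difference is not statistically significant, and confirm from the source that the progression-free survival row is rightly left without one.

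The cost is one sentence in the leaflet image, one or two in the appendix, and a slightly longer table cell. Sample size, outcomes and analyses do not change. If responses have already been collected with the present wording, the leaflet as shown cannot be corrected; the missing note should then be reported as a limitation when questions 13 and 14 are interpreted.

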For participants randomized to receive the EMA's proposed key information section with qualitative statements, we developed a version based on the draft proposal published by the EMA.⁹ The proposed key information section summarizes the goal of treatment, main benefits, contraindications, and most serious side effects. To ensure accuracy of our interpretation, we sought feedback from the EMA. The final version tested in the trial incorporated their suggestions.

Next, we developed a key information section that includes quantitative data on the drug's main benefits and side effects, modeled on the Drug Facts Box – a tabular summary format for prescription drugs, designed to resemble a nutrition label.¹³ The key information section presents qualitative information about the drug (including its indication and treatment goal), and how it was studied (the comparator treatment and number of patients enrolled in the clinical trial that supported the drug's approval). It supplements this with quantitative data the drug's benefits and side effects. Data on the drug's benefits and side effects were sourced from European Public Assessment Reports (EPARs). Further details are provided in the appendix.

Procedure

Upon entering the study, participants will be randomized to 1 of 3 versions of a patient leaflet. The patient leaflet is for tivozanib (Fotivda), a cancer drug approved by the EMA for the treatment of advanced kidney cancer. An electronic version of the patient leaflet along with a download link will be displayed alongside each multiple-choice question. Participants will first complete a practice question designed to test their ability to scroll through and navigate the leaflet. Participants who answer the practice question incorrectly will be excluded from the study at this stage.

The first set of questions is designed to evaluate participants' expectations, perceived magnitude, and understanding of the drug's benefits and side effects based on the information provided in the patient leaflet. To assess expectations, we will ask participants about the likelihood that patients with advanced kidney cancer would be cured, live longer, or

feel better if they were treated with tivozanib. They will also be asked about the perceived magnitude of the tivozanib's benefits and side effects.^{13–15}

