To assess understanding, we will ask participants 3 questions: (1) the approved indication of tivozanib, (2) the most common serious side effect associated with treatment, and (3) the recommended dose of treatment. Answers to all 3 questions can be found in the standard patient leaflet. Information about the drug's indication is also included in both key information sections; information about the most common serious side effect is presented in the EMA's proposed key information section with qualitative statements. Participants randomized to the key information section with both qualitative statements and quantitative data will receive 2 additional questions: one asking them to identify the difference in overall survival between tivozanib and standard treatment, and another asking about the difference in serious side effects.

Next, all participants will be asked a series of questions to assess their satisfaction with the information presented in the version of the patient leaflet they were assigned. Before ending the survey, we will ask participants for information about their demographics: their age, sex, highest level of educational attainment, and personal experience with cancer (whether themselves, an immediate family member or close friend had been diagnosed with cancer).

Primary outcome

The primary outcome of the study is participants' expectations about the drug's benefits and side effects. We selected tivozanib as the test treatment because it is representative of many recently approved cancer drugs. Tivozanib is not curative for advanced kidney cancer and, at the time of approval, it demonstrated no additional overall survival or quality of life benefit relative to standard treatment (sorafenib). Owing to the lack of information about drug benefits in the standard patient leaflet and the limited information quantifying side effects, we hypothesized that participants would overestimate the benefits and underestimate the side effects of tivozanib.¹⁴

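### The practice question (Q3) sends every participant to the leaflet section that holds the answer to Q15, which weakens Q15 as a measure of locating information in the leaflet body

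*Combined protocol and SAP*

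**What the plan says.** **Order of events.** Under Procedure: "Upon entering the study, participants will be randomized to 1 of 3 versions of a patient leaflet". The practice item follows, before any outcome question: "Participants will first complete a practice question designed to test their ability to scroll through and navigate the leaflet". Its consequence is stated there too: "Participants who answer the practice question incorrectly will be excluded from the study at this stage". Quality control repeats the exclusion.

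**The practice item.** Survey Section B, Q3: "This first question is practice. Scroll to section 3 of the leaflet and find the first word". There are four response options. The leaflet's contents list (Figure 1) gives section 3 the title How to take Fotivda.

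**The outcome item.** Survey Section B, Q15, is put to all groups: "What is the recommended dose of Fotivda during the first 3 weeks of treatment". The answer key notes "correct; answer in section 3 of PIL".

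**How Q15 is used.** Procedure lists the dose as one of three understanding questions and says of them: "Answers to all 3 questions can be found in the standard patient leaflet". Under Secondary outcomes, each comprehension question is analysed by comparing the proportion correct across the arms.

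**Leaflet access.** "An electronic version of the patient leaflet along with a download link will be displayed alongside each multiple-choice question". Nothing in the plan comments on Q3 and Q15 sharing a section.

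**The concern.** The leaflet stays on screen, so a correct answer to Q15 depends partly on finding the right section and partly on finding and recognising the dose within it. Q3 acts on the first part. It takes every participant to section 3, under a heading about how to take the medicine, and removes those who answer wrongly. A practice item meant only to confirm that people can navigate thus rehearses the location of one outcome answer.

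This matters because of where Q15 sits among the comprehension items. The trial adds a section to the front of the leaflet, and a natural question is whether that addition changes how well people use the rest. Q15 is the one shared item that every arm has to answer from the body. If Q3 has already evened out the arms in reaching section 3, a null Q15 result could be taken to mean that a key information section does not affect use of the leaflet body, when the practice task had helped to produce it.

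**Working it through.** **Step 1. Where each shared comprehension answer can be found** (Procedure; Figure 1; Survey Section B)

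| Item | Control | EMA qualitative arm | Quantitative arm | Does Q3 lead to that place in the body? |
|---|---|---|---|---|
| Q4, indication | body | key information section or body | key information section or body | no (section 1) |
| Q12, most common serious side effect | body | key information section or body | body | no (section 4 by its title) |
| Q15, dose | body | body | body | yes (section 3) |

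Neither key information section in Figure 1 states the dose. Q15 is therefore the only item answered from the body in all three arms. Q12 is a body item for control versus quantitative, but not for contrasts that involve the EMA arm.

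**Step 2. What Q3 does to Q15.** Two mechanisms operate.
- *Cue:* everyone has been to section 3 before Q15.
- *Screen:* people who answer Q3 wrongly are not analysed. The screen comes after randomisation and uses the assigned leaflet, so the Q15 comparison is conditional on passing, and pass rates may differ by arm.

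Neither mechanism acts on finding or recognising the dose once in section 3.

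**Step 3. The plan's own figure.** The plan states no figure for Q15. The 700 per group is for the primary outcome, at 60% vs 50%, 90% power and alpha 0.05/3 = 0.0167. The pooled-variance formula is

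n = [z(α/2)·√(2p̄(1−p̄)) + z(β)·√(p1(1−p1) + p2(1−p2))]² / (p1−p2)², with p̄ = 0.55.

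It gives 667 per group, or 686 with continuity correction. Power at 700 is 91.5%. The 700 is reproduced and is used below as the number per arm.

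**Step 4. Illustration; every rate here is an assumption.** Let
- f = share who would reach section 3 unaided, differing by 10 points between arms (80% vs 70%, or 90% vs 80%);
- c = 0.85, proportion correct once in section 3, equal in both arms;
- g = proportion correct among those who do not reach it, 0 or 0.20;
- k = share of the failure to reach section 3 that cue and screen together remove.

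The share reaching section 3 becomes F = f + k(1−f), and P(correct) = F·c + (1−F)·g. The arm difference is then (1−k)·(f0−f1)·(c−g).

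| k | g = 0 | g = 0.20 | Power, 700 per arm, two-sided 0.05 |
|---|---|---|---|
| 0 | 0.10 × 0.85 = 8.5 points | 0.10 × 0.65 = 6.5 points | 75% to 95% |
| 0.5 | 4.25 points | 3.25 points | 30% to 49% |
| 1 | 0 | 0 | not applicable |

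Correct answers rise in both arms as k rises. With f = 80% vs 70% and g = 0, they go from 68.0% vs 59.5% at k = 0 to 76.5% vs 72.25% at k = 0.5.

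**Step 5. What is left untouched.** A difference that arises inside section 3 passes through. At 700 per arm, 85% vs 80% still has about 69% power, and 80% vs 70% about 99%.

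**The case against.** A reader might infer that Q15 can no longer show any effect of leaflet version on use of the body. The documents do not support that. Q3 asks only for the first word of a numbered section and does not mention dosing. Q15 comes twelve question numbers later. Participants must still recognise which section they need, find the dose and choose among four doses and a not-sure option. The contents list already signposts section 3, so the cue may add little, and a four-option check can be passed by guessing. A gap of exactly zero appears only if k = 1 and accuracy within section 3 is equal in the arms, and both are assumptions.

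Nor is Q15 the only item that bears on use of the body. Q12 does so for control versus quantitative, and Q3 does not point to its section. Q16 asks about ease of finding information, though only by self-report.

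The plan also labels Q15 as understanding. It states no aim of testing whether a front section distracts from the rest, and it does not plan to read a null result that way. This stands, and it limits the weight of the point. It does not remove it: participants are told to answer from the leaflet, so locating the dose is part of answering correctly.

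Finally, moving Q3 elsewhere leaves a navigation screen after randomisation. That is correct, and the fix should not be credited with removing it.

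**Conclusion.** The point holds as a limited weakness in one secondary item. Q3 cues and screens on the section that contains the Q15 answer. This tends to raise correct Q15 answers in all arms and to weaken Q15, towards no difference, as a measure of locating information in the leaflet body. Differences arising within section 3 stay measurable.

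The size cannot be derived from the documents. On the assumed rates, the section-finding part of the arm difference could be anywhere from intact (6.5 to 8.5 points) through halved (3.3 to 4.3 points) to absent. The separate contributions of cue and screen cannot be told apart. The primary outcome (Q5 to Q7) and the 700 per group are unaffected. The change is worth making because the overlap is avoidable at almost no cost.

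**What to change.** Point Q3 to a section that holds no outcome answer, for example section 5 (How to store Fotivda), with a new correct word and matching distractors. Avoid sections 1, 3 and 4, where the answers on indication, dose and side effects sit.

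This removes the section-specific cue. General selection on navigation ability after randomisation remains, so also report the number failing Q3 in each arm.

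The cost is one question stem and its options in Qualtrics, plus one line in the participant flow. No participants, survey length or analyses are added. Section 5 lies further into the leaflet, so slightly more people may fail the check.

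If data collection has begun, leave the survey as it is. Report that Q15 followed a practice task in the same section, and do not read a null Q15 result as evidence that a key information section leaves use of the leaflet body unchanged.
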